### The microbiome of the pouch

It has previously been shown that up to 60-80% of pouch microbiota cannot be cultured (30), and this has complicated microbiome studies greatly. Culturing bacteria of the gastrointestinal tract greatly favors aerobic bacteria, which can result in misleading findings. The development of 16S rRNA (16S ribosomal ribonucleic acid) sequencing has revolutionized microbial diagnostics. It allows detection and quantification of non-culturable as well as slow-growing bacteria in both a clinical and research setting. However, it does not assess the viability of the detected bacteria.

Studies have shown considerable differences between bacteria found in the pouch lumen and feces, and bacteria adherent to the mucosa (31,32). Especially the bacteria found in the mucosa are thought to be involved in the pathogenesis of IBD and pouchitis because they are in close contact with the host and the immune system (31,33).

Tissue biopsies from the pouch mucosa will be analyzed in our study for change in bacterial composition with 16S rRNA sequencing.

It is still unclear which bacteria are responsible for the development of pouchitis, but several bacteria have been associated with inflammation whereas others usually found in healthy pouches disappear or are reduced in number in pouchitis. In general, it is thought that a lower bacterial diversity leads to inflammation. Enterobacteriaceae, streptococci, Bacteroidetes, and enterococci are thought to be involved in the maintaining of gut homeostasis, and low levels of these bacteria favor the development of pouchitis (34). As opposed to this, a higher incidence of proteobacteria and sulfate-reducing bacteria such as clostridia are found in the inflamed pouch (35–37).

Bacteria increased in pouchitis	Bacteria in healthy pouches or reduced in pouchitis
Proteobacteria Clostridia (especially C. perfringens ) Bacteroidaceae Roseburia Akkermansia Escherichia coli (AIEC) (38)	Bacteroidetes Faecalibacterium prausnitzii Veillonella Staphylococci Enterobacteriaceae Streptococci Enterococci Bifidobacteriaceae Eubacteriaceae Bacillaceae Moraxellaceae Burkolderaceae Corynebacteriaceae Sutterella
Inconclusive	
Lachnospiraceae Ruminococcus	

Fusobacterium
----------------------

Table 1: Overview of bacteria associated with pouchitis

*Roseburia* is a genus of anaerobic Gram-positive bacteria, which are found in increased numbers in the inflamed pouch. They are motile, being flagellated. The protein flagellin from the bacterial flagellum induces proinflammatory gene expression by activating TLR-5 (Toll-like-receptor 5) (35). *Akkermansia* is a genus of mucin-degrading bacteria also associated with the development of pouchitis (39).

Butyrate-producing bacteria such as *F. prausnitzii* are found more often in healthy pouches. The butyrate is an important energy source for colonic epithelial cells, has anti-inflammatory properties and improves the barrier function of the epithelial cells. Pouchitis is associated with a decrease in these bacteria (40).

### Targeting dendritic cells in pouchitis and bacterial dysbiosis

GM-CSF (granulocyte-macrophage colony stimulating factor) is a glycoprotein cytokine that stimulates the production, survival, activation and differentiation of white blood cells – granulocytes and monocyte/macrophages. A deficiency of GM-CSF has been shown in previous studies to induce inflammation in animal models with Crohn’s disease, as well as being associated with an impaired intestinal barrier function (41–43). When administered intraperitoneally in mice, it has been shown to decrease the number of pro-inflammatory cytokines in the mucosa in experimental colitis and improve healing (44–46). It has recently been shown that GM-CSF might also be involved in a genetic component of Crohn’s disease involving decreased signaling in macrophages and monocytes (47,48).

Anti-GM-CSF antibody concentrations also seem to be increased in IBD patients experiencing increased disease activity, especially in Crohn’s disease (49).

Several phase 1 studies have shown an ameliorating effect of systemic GM-CSF in Crohn’s disease, whereas one study has not (3–6). Moreover, GM-CSF has shown a beneficial effect in some cases of fistulizing Crohn’s disease, and with fistulization being a known problem in pouchitis, this holds promise for a possible beneficial effect in patients with this condition. However, systemically administered GM-CSF, e.g. given subcutaneously, may not produce a sufficient local effect in the bowel, while overstimulating the bone marrow and causing side effects such as bone pain (50).

GM-CSF is secreted by various cells in response to proinflammatory stimuli and binds to the GM-CSF receptor on myeloblastic cells. The complex mechanisms behind its multiple functions are not yet fully understood, but it is known to activate at least three different pathways: JAK/STAT (Janus kinase/signal transducer and activation of transcription), MAPK (mitogen-activated protein kinase) and PI-3 (phosphatidylinositol 3) (46).

In the intestine, GM-CSF has been found to have multiple effects on the mucosa:

- It enhances the expression of costimulatory molecules in APCs such as dendritic cells and thereby induces mucosal immunity (51).
- In mice, it has been shown that a GM-CSF deficit was associated with an increased inflammation of the ileum after exposure to NSAID. It is assumed that GM-CSF plays a role in regulation and survival of intestinal epithelial cells and thereby upholds the intestinal barrier (42).

GM-CSF acts physiologically as a cytokine, by paracrine action on neighboring or nearby cells in the same tissue compartment. It does not readily cross tissue barriers, and only when used pharmacologically at

supraphysiological doses does it begin to act at a distance like a classical hormone. This means that systemically administered GM-CSF will act principally on the bone marrow and only to a lesser extent on the granulocytes and macrophages found in peripheral tissues. At the same time, the mucosal macrophage populations of large organs like the lungs (e.g. the pulmonary alveolar macrophages) and gut (gut mucosal macrophages) are semi-independent cell populations which only interchange slowly and incompletely with the monocytes of the circulation. Indeed, a population of self-maintaining gut macrophages has been described that occupies microanatomical niches in the gut submucosa and myenteric plexus and appears to be essential for intestinal homeostasis (52). For GM-CSF to have an effective restorative effect on defective gut macrophage function in clearing microorganisms and maintaining the mucosal barrier, it should be given locally, so that it can reach the local macrophages at an adequate concentration.

Besides treatment with GM-CSF, treatment would also include a combination of the antibiotics metronidazole and fosfomycin. Metronidazole is a common antibiotic used against anaerobic bacteria, where it disrupts DNA-synthesis (53). Fosfomycin is an antibiotic that is used against both Gram-positive and Gram-negative bacteria in that it inhibits bacterial wall synthesis (54).

Fosfomycin is the international non-proprietary name of a broad-spectrum antibiotic isolated and characterized in 1969 from *Streptomyces fradiae* strains under the name phosphomycin or phosphonomycin (55). Its structure was determined to be (-)(1R, 2S)-1,2-epoxypropylphosphonic acid (56) with the systematic IUPAC (International Union of Pure and Applied Chemistry) name [(2R,3S)-3-methyloxiran-2-yl]phosphonic acid and a formula weight of 138.1 Da. Fosfomycin is bactericidal and inhibits bacterial cell wall biosynthesis by inactivating the enzyme UDP-N-acetylglucosamine-3-enolpyruvyltransferase, also known as MurA (57). This enzyme catalyzes the committed step in peptidoglycan biosynthesis, the ligation of phosphoenolpyruvate to the 3'-hydroxyl group of UDP-N-acetylglucosamine to form N-acetylmuramic acid. Fosfomycin is a phosphoenolpyruvate analogue that inhibits MurA by alkylating an active site cysteine residue. The antibiotic enters the bacterial cell via the glycerophosphate transporter.

Given this mechanism of action, fosfomycin has a broad bactericidal spectrum, being active against aerobic genera such as *Staphylococcus*, including MRSA (Methicillin-resistant *Staphylococcus aureus*), *Streptococcus*, *Enterococcus*, *Neisseria*, *Escherichia*, including ESBL (extended-spectrum  $\beta$ -lactamase-producing *E. coli*), *Proteus* (indole-negative), *Serratia*, *Salmonella*, *Shigella*, *Pseudomonas*, *Haemophilus*, and *Vibrio*, less active against indole-positive *Proteus* spp., *Klebsiella* and *Enterobacter* spp. It is also active against the anaerobic genus *Fusobacterium*, as well as the anaerobic genera *Peptostreptococcus* (including *Peptoniphilus*, *Fingoldia* and *Anaerococcus*). However, it is inactive against the anaerobic *Bacteroides fragilis* group of bacteria.

There is a low prevalence of bacterial resistance to fosfomycin in the community, and studies of the prevalence of resistant bacteria after the introduction of fosfomycin have shown either no increase or only a modest increase in the prevalence of resistant organisms. However, prolonged exposure to the antibiotic may enable bacteria to develop resistance by selection of mutants that lack the glycerophosphate transporter pathway. Alternative mechanisms of resistance involve the loss of the inducible hexose phosphate transporter, a Cys-Asp mutation in MurA, or acquisition of plasmids coding for the fosfomycin inactivating enzymes *fosA* and *fosB* (in addition to the chromosomal *fosX* in *Listeria monocytogenes*). The mutant strains may, however, also show reduced pathogenicity (58). This may explain why the emergence of bacterial resistance is seen on prolonged exposure *in vitro*, but much less frequently *in vivo*. The appearance of resistant bacterial strains in controlled clinical trials of orally or

intravenously administered fosfomycin has been 3.0% overall, with a maximum of 15% for *Pseudomonas aeruginosa*. In general, fosfomycin is seen to be a valuable addition to the therapeutic armament against multidrug-resistant organisms.

Fosfomycin has been shown to have the capacity to favor phagocytosis and act as an immunomodulator. It is accumulated by polymorphonuclear leukocytes to reach concentrations that are up to twice those of the extracellular fluid, but does not affect their cellular functions, while still exerting a bactericidal effect on *Staphylococcus aureus* (59).

Fosfomycin is also actively taken up by intestinal mucosal cells to reach concentrations that can kill intracellular bacteria such as Fusobacteria. A rapid uptake of fosfomycin has been demonstrated in IPEC-J2 cells (Intestinal porcine enterocyte J2 cell line) exposed to fosfomycin calcium at 580 µg/ml to reach an intracellular concentration approaching 30 µg/ml within 15 minutes (60). This concentration of fosfomycin is readily reached by local administration to the gut mucosa.

Fosfomycin is known to penetrate readily through tissue barriers and into bacterial biofilm (61) so that high, bactericidal concentrations of fosfomycin will result from the direct application of fosfomycin solution to the pouch mucosa. Fosfomycin inhibits the adhesion to epithelial cells of various bacterial species, including those involved in biofilm formation (62).

Fosfomycin shows considerable synergism in bactericidal effect on a large number of strains of organisms from the susceptible genera mentioned, when used in combination with a large number of antibiotics of the penicillin, cephalosporin, aminoglycoside, macrolide and lincosamide types. While early studies showed a synergistic effect on about 70-100% of tested strains for various antibiotic combinations, subsequent more extensive studies showed synergy rates of 36-74%. The remaining strains showed merely additive effects and an inhibitory effect was only seen in one or two individual antibiotic combinations on an individual bacterial strain (62). The fact that fosfomycin shows synergy with many individual antibiotics and indeed abrogates the toxicity of many other antibiotics, including the nephrotoxicity and ototoxicity of the aminoglycosides, favors the use of fosfomycin in combination with other antibiotics to produce a potent bactericidal action and compensate for any development of fosfomycin resistance during more prolonged treatment.

Metronidazole is a semi-synthetic antibiotic which is active against a number of anaerobic bacteria including bacteria of the *B. fragilis* group and *Fusobacterium* spp. Oral metronidazole, alone or in combination with oral ciprofloxacin is one of the standard treatments for pouchitis (63). It has also been used systemically in combination with systemic fosfomycin for prophylaxis against wound infection after abdominal surgery. The intracellular penetration of metronidazole appears to be by rapid passive diffusion, so that intracellular levels approach equilibrium with extracellular levels within 15 minutes (63). It is a part of the study drug combination in the present study, in which it will be locally applied at a low dose to the pouch mucosa to reach a higher concentration than that which can be achieved by conventional oral administration, to reduce the bacterial load of toxin-producing *B. fragilis* group bacteria which may play a role in pouchitis and which would not be susceptible to the locally applied fosfomycin.

Potential risks of the study include the relatively low risk of endoscopy of the pouch, as well as any potential analgesic medicine given during the procedure. The low dosage and local application of the study drug combination is also deemed to be of low risk to the patients. Previous studies have tested higher dosages of the same combination with intraperitoneal application of the drug, without serious adverse reactions. The safety of application of a lower dosage in the pouch will be the subject of Phase I of this study. A more thorough description of all side effects of GM-CSF, Fosfomycin and metronidazole is given in chapter three.

Potential benefits of the study include a potential new treatment for pouchitis, as well as a better understanding of the role of bacteria in pouchitis. Moreover, administering a combination drug locally in the pouch instead of systemically will potentially enable lower dosage and lessen side effects.

### 3. Study objectives

The hypothesis of the study is that both systemically administered GM-CSF (given subcutaneously) and systemically administered antibiotics (given orally) respectively act relatively weakly, when given at tolerable doses, on the immunocompetent cells of the bowel mucosa and the bacterial dysbiosis that contributes to the pathogenesis of pouchitis. It is hypothesized that the beneficial action of these agents will be potentiated if they are administered locally into the pouch at higher concentrations than can be achieved with systemic administration at acceptable doses. At the same time, the total daily local doses of these agents will be considerably lower than the conventionally used systemic doses, and their limited absorption from the pouch will significantly reduce the systemic side effects of conventional pouchitis treatment.

We aim to investigate whether GM-CSF in combination with metronidazole and fosfomycin, applied topically in the pouch, can be used in patients with pouchitis. As pouchitis seems to mimic Crohn's disease, and responds to therapy used in Crohn's disease, we suspect that this combination therapy can target the bacterial dysbiosis and inadequate immune response in pouchitis.

The therapy will be applied topically, both under endoscopic supervision in an initial safety study and depending on safety data, later by daily administration for one week using an enema in the pouch in a proof of concept study. We will investigate if this therapy has an effect on pouchitis by assessing if the patient has a lowering in the Pouchitis Disease Activity Index, by clinical history and examination, taking biopsies from the pouch mucosa and taking blood samples.

#### Phase I – Safety study

##### Primary outcome measure

- Safety: Determine serious adverse reactions or adverse reactions from the application of GM-CSF, metronidazole and fosfomycin in the pouch as seen in Appendix 8. The category of the reactions will be determined by the principal investigator according to the safety assessment described in chapter 7.  
A summary of the product characteristics of GM-CSF, fosfomycin and metronidazole will function as a reference document in evaluation of adverse effects. We will monitor adverse reactions from the day of the intervention in Phase I and II until respectively day 30 and 37. The safety of the intervention will be measured by adverse reactions.

##### Secondary outcome measures

- Change in the pouchitis disease activity index (PDAI) – A decrease of 3 points or more will be determined as an improvement in PDAI from before application of the study drug to 7 days after application of the study drug
- Change in median WBC, CRP, creatinine and liver enzymes from before application of the study drug to 7 days after application of the study drug
- Change in microbial diversity in the pouch using 16S rRNA sequencing from before application of the study drug to 7 days after application of the study drug

## Phase II – Proof of concept study

### Primary outcome measure

- Change in the pouchitis disease activity index (PDAI) – A decrease of 3 points or more will be determined as an improvement in PDAI from before application of the study drug to 7 days after application of the study drug

### Secondary outcome measures

- Change in the clinical, endoscopic or histological PDAI – A decrease of 3 points or more will be determined as an improvement in PDAI from before application of the study drug to 7 days after application of the study drug
- Change in median WBC, CRP, creatinine and liver enzymes from before application of the study drug to 7 days after application of the study drug
- Change in microbial diversity in the pouch using 16S rRNA sequencing from before application of the study drug to 7 days after application of the study drug
- Safety: Determine serious adverse reactions or adverse reactions from the application of GM-CSF, metronidazole and fosfomycin in the pouch as seen in Appendix 8.

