## Appendices

### Appendix 1 – PDAI

Criteria	Score
Clinical	
Stool frequency	
Usual postoperative stool frequency	0
1–2 stool/day >postoperative usual	1
≥3 stools/day >postoperative usual	2
Rectal bleeding	
None or rare	0
Present daily	1
Faecal urgency or abdominal cramps	
None	0
Occasional	1
Usual	2
Fever (temperature >37.8°C)	
Absent	0
Present	1
Endoscopic inflammation	
Oedema	1
Granularity	1
Friability	1
Loss of vascular pattern	1
Mucous exudate	1
Ulceration	1
Acute histological inflammation	
Polymorphonuclear leucocyte infiltration	
Mild	1
Moderate+crypt abscess	2
Severe+crypt abscess	3
Ulceration per low power field (mean)	
<25%	1
25–50%	2
>50%	3

Table 1: Pouchitis Disease Activity Index (PDAI). A score of 7 or higher is diagnostic of pouchitis.

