### Appendix 3 – Enrollment form

Name:

Address:

Telephone no:

Date of birth
Gender
Year diagnosed with ulcerative colitis
Year of IPAA surgery
Allergies
Past medical history  COPD  Others  Diabetes  Asthma  Hypertension  Ischemic heart disease  Liver disease  Neurological diseases
Medicine
Past medicine used for pouchitis  Metronidazole  Ciprofloxacin  Ampicillin  Piperacillin  Probiotics  Others
Diets used for pouchitis

Protocol code no: 2020-01-GMF-1  
EudraCT no: 2020-000609-10

Clinical PDAI to be filled in at enrollment:

Criteria	Score	Patient score
Clinical		
Stool frequency		
Usual postoperative stool frequency	0	
1-2 stools/day > than postoperative usual	1	
>3 stools/day > postoperative usual	2	
Rectal bleeding		
None or rare	0	
Present daily	1	
Fecal urgency or abdominal cramps		
None	0	
Occasional	1	
Usual	2	
Fever (temperature > 37.8)		
Absent	0	
Present	1	
Total	6	

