## Appendix 4 – Endoscopy 1, Phase I and II

Patient name:

Date:

Endoscopic PDAI to be filled in:

Criteria	Score	Patient score
Endoscopy		
Endoscopic inflammation		
Edema	1	
Granularity	1	
Friability	1	
Loss of vascular pattern	1	
Mucous Exudate	1	
Ulceration	1	
Total	6	

Endoscopy complications: \_\_\_\_\_

Did the patient receive analgesia/sedation

No

Yes, which: \_\_\_\_\_

Biopsies taken for histology: \_\_\_\_\_

Biopsies taken for microbiology: \_\_\_\_\_

GM-CSF Metronidazole/Fosfomycin applied: \_\_\_\_\_

Medical complications: \_\_\_\_\_

Date                      Place

Endoscopy physician:

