## Appendix 6 – Histology

Patient name:

Date:

Histological PDAI to be filled in:

Criteria	Score	Patient score
Histology		
Acute histological inflammation		
Polymorphonuclear leucocyte infiltration		
Mild	1	
Moderate + crypt abscess	2	
Severe + crypt abscess	3	
Ulceration per low power field (mean)		
<25%	1	
25-50%	2	
>50%	3	
Total	6	

Date                      Place

Pathologist:

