## Appendix 7 – Patient PDAI overview

Patient name:

Criteria	Score	Patient score before treatment Date:    /    /   	Patient score after treatment Date:    /    /   
Clinical			
Stool frequency Usual postoperative stool frequency 1-3 stools/day > than postoperative usual >3 stools/day > postoperative usual	0 1 2		
Rectal bleeding None or rare Present daily	0 1		
Fecal urgency or abdominal cramps None Occasional Usual	0 1 2		
Fever (temperature > 37.8) Absent Present	0 1		
Endoscopic inflammation Edema Granularity Friability Loss of vascular pattern Mucous Exudate Ulceration	1 1 1 1 1 1		
Acute histological inflammation Polymorphonuclear leucocyte infiltration Mild Moderate + crypt abscess Severe + crypt abscess Ulceration per low power field (mean) <25% 25-50% >50%	1 2 3 1 2 3		
Total	18		

Date                      Place

Examiner:

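### The 3-point improvement threshold of the 18-point total PDAI is applied unchanged to the 6-point subscores, where a baseline of 0 to 2 can never count as improved

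*Protocol*

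**What the plan says.** The Phase II primary outcome in section 3 is "Change in the pouchitis disease activity index (PDAI) – A decrease of 3 points or more will be determined as an improvement in PDAI". This refers to the whole index.

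The first Phase II secondary outcome carries the same clause over to the three parts of the index: "Change in the clinical, endoscopic or histological PDAI – A decrease of 3 points or more will be determined as an improvement in PDAI". No reason is given for using one threshold on both scales. The text does not say whether the three parts are separate outcomes or alternatives within one outcome.

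The scoring forms fix the ranges. Appendix 3 (clinical), Appendix 4 (endoscopic) and Appendix 6 (histological) each show a maximum of 6. Appendix 7 shows a maximum of 18 for the total. Appendix 1 adds "A score of 7 or higher is diagnostic of pouchitis". The inclusion criteria in section 5 ask for a diagnosis of pouchitis and set no minimum total or subscore.

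Section 8 plans to describe pre- and post-treatment differences by mean and standard deviation or by median and range. Tests are parametric or non-parametric according to the distribution. Section 8 links the 3-point fall to the primary objective and mentions no responder analysis by subscore.

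**The concern.** The subscores are there to show where any benefit lies: in symptoms, in the endoscopic picture or in the tissue. With the copied threshold, a patient's status on a subscore depends on how the baseline points happen to be spread over the three parts, as well as on whether that part healed. A part that begins low is recorded as not improved whatever happens to it.

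This matters most for histology. The Bias paragraph in section 3 notes that the pathologist is blinded to whether a sample was taken before or after treatment. Histology is the only blinded part of the PDAI in an open-label, single-arm study, so it is the most credible part. It is also a part on which patients with active but limited inflammation can fall below the threshold at baseline.

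**Working it through.** **Inputs.** Item scores are from Appendix 1 and maxima from Appendices 3, 4, 6 and 7. The threshold is from section 3. The diagnostic score of 7 is from Appendix 1.

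**1. Ranges reproduced.**
- Clinical: 2 + 1 + 2 + 1 = 6.
- Endoscopic: six items of 1 point = 6.
- Histological: 3 + 3 = 6.
- Total: 6 + 6 + 6 = 18.

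All agree with the forms. The protocol offers no figure in support of the subscore threshold that could be reproduced.

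**2. Relative size of the threshold.** On the total, 3/18 = 17%. On a subscore, 3/6 = 50%.

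**3. Floor.** A fall of 3 needs a baseline of at least 3, so baseline values 0, 1 and 2 are excluded. For all three subscores to be able to respond, the total must be at least 3 + 3 + 3 = 9. At a total of 7 or 8, at least one subscore cannot meet the rule. Only from a total of 15 are all three always able to respond, since a subscore of 2 or less caps the total at 2 + 6 + 6 = 14.

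**4. Example.** A patient scores 3/2/2 at baseline (total 7) and 0/0/0 after treatment. The total falls by 7 and the primary rule is met. The first subscore falls by 3 and counts as improved. The other two fall by 2, to zero, and count as not improved.

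**5. Histology.** Two items scored 0 to 3 give 4 × 4 = 16 combinations. Those summing to 0, 1 or 2 number 1 + 2 + 3 = 6. Moderate infiltration with crypt abscess and no ulceration scores 2. So does mild infiltration with ulceration below 25%. Neither can become a histological responder.

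**6. Score patterns (not patients).** Giving every combination of three subscores equal weight, the share in which a given subscore is below 3 is:

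| Baseline total | Patterns | Given subscore < 3 |
|---|---|---|
| 7 | 33 | 19 (58%) |
| 9 | 37 | 15 (41%) |
| 11 | 33 | 9 (27%) |

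Over all 259 patterns with a total of at least 7, the number with every subscore at 3 or more is 4 × 4 × 4 = 64. So 195/259 = 75% have at least one subscore that cannot respond. Weighting by item combinations gives 69%. These figures describe the scale. They do not estimate how many trial patients are affected.

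**7. The two readings of *or*.** If the parts are three separate outcomes, the floor applies to each. If improvement on any one part is enough, the floor does not exclude anyone with a total of at least 7: three subscores of at most 2 sum to at most 6, so one must be 3 or more. The composite result then does not show which part improved.

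**The case against.** The strongest reply is that the outcome is headed as a change, and section 8 already plans paired description and testing of pre/post differences. Numeric subscore changes would probably be reported in any case, and the floor does harm only if the responder label replaces them. The clause also speaks of improvement in PDAI, so it could be read as still meaning the total. Much of this stands, and it is why the remedy is cheap. It does not rescue the clause. Applied to the subscores, it misclassifies complete healing. Applied to the total, it merely repeats the primary outcome. How a SAP might settle the *or* is not known, but the threshold itself is fixed in the protocol.

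Two stronger inferences are tempting and unsupported.

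- **That many patients are affected.** The protocol gives no baseline distribution, and the shares above are shares of score patterns.
- **That *or* gives chance three tries.** Suppose no effect and an SD of 1.5 for subscore change (an assumption; the documents give none). The chance of a fall of 3 on one subscore is P(Z > 2.5/1.5) = 4.8%, and 1 − (1 − 0.048)³ gives about 14% for any of three. That formula lets all three subscores fall by 3, which the floor forbids for many patterns. At total 7, 24 of 33 patterns have one eligible subscore and 9 have two, so the rate is 24/33 × 4.8% + 9/33 × (1 − 0.952²) = 6.0%. On the same basis it is about 8% at total 9 and 10% at total 11. The total-score rule under the same independence assumption has a chance rate of about 17%. Only with an SD of 2, uncorrelated changes and no floor did the any-of-three rate exceed it (28.5% against 23.7%). The three-tries argument also applies only to the composite reading, whereas the floor bites mainly when the outcomes are separate.

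**Conclusion.** The point holds as a defect in how a secondary outcome is defined. A threshold set for a 0–18 scale is carried without justification to 0–6 scales, and subscores of 0 to 2 are thereby classed as not improved whatever happens to them. That every patient at a total of 7 or 8 has at least one such subscore is arithmetic and rests on no assumption. The number of patients affected cannot be stated. The undefined *or* adds ambiguity: one reading is exposed to the floor, and the other hides which component changed. No claim of inflated chance findings is made.

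The effect is limited to interpreting the subscores in a 12-patient, single-arm proof-of-concept phase. The primary outcome, the sample size and the safety assessment are untouched.

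**What to change.** Keep the 3-point rule for the total PDAI and delete it from the subscore bullet. Name the clinical, endoscopic and histological subscores as three separate secondary outcomes. Analyse each as a paired numeric change, reporting the median change with its range or a confidence interval and a Wilcoxon signed-rank test. This agrees with the pre/post description and non-parametric testing already foreseen in section 8.

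The cost is a change of wording; no extra data, visits or patients are needed. The one loss is a responder percentage per subscore. If the investigators want to keep such a percentage, the protocol should justify a threshold for a 0–6 scale, state whether *or* means separate outcomes or any one of three, and say how patients with a baseline subscore below the threshold are counted.
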